6.1.2 Treatment Phase

The 10 fingernails of each participant will be randomly assigned to treatment with platelet-rich plasma or platelet-poor plasma (placebo) treatment groups in a 8:2 ratio using a computer-generated randomization scheme developed by the data manager.

Study Visits Visit 1: Week 0 - 2

Subjects who fulfill all inclusion and exclusion criteria, and sign informed consent are eligible to enroll and begin Visit 1 procedures that same day. For those patients that do not have a negative histopathology result for onychomycosis within the past 6 months, a nail clipping is obtained during screening visit and visit 1 procedure will take place in week 2 assuming the patient fulfill all inclusion and exclusion criteria.

Visit 1 Procedures:

- Patient Instructions
- Take High resolution digital photographs
- Randomization of participants that fulfilled all inclusion and exclusion criteria
- First Injection of PRP

Visits 2 and 3: Week 4 - 6 (±7 days) and Week 8 - 10 (± 7 days) The following procedures will be performed on these visits:

Second and third injections of PRP

- Review of eligibility criteria including review of concomitant medications/cosmetics
- · Collection of adverse events
- Take High resolution digital photographs

Visit 4: Week 12 – 14 (± 7 days) Collection of adverse events

- Take High resolution digital photographs
- Collection of Patient Satisfaction Survey

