12.1 Study Design/Endpoints

For study design, please see section 3. Study Design.

Endpoints

The Primary efficacy endpoint will be the Physician Global Improvement Assessment (PGIA), which will be compared between follow-up point (week 12 - 14) and baseline point for nails with PRP injection, and between follow-up point (week 12 - 14) and baseline point for nails without PRP injection. The power analysis estimated that with approximately 44 nails with PRP injection enrolled in the study, a score change of 0.5 from baseline to week 12 – 14 can be detected through paired two-sided t-test with 90% power at 0.05 significant level for PRP group. The calculation assumed a standard deviation of 1 in scores. PGA is a novel tool that there is not enough reference to assume an accurate standard deviation, so the sample size estimation was also performed on a range of sd assumption. With assumption of sd in range of 0.5 to 1, 13 to 97 nails would be needed for the PRP injection group to detect a score change of 0.5 from baseline to week 12 - 14 through paired two-sided t-test with 90% power at 0.05 significant level.

Sample size estimation summary given different settings of standard deviation and meaningful changes

	sd=0.5	sd=1	sd=1.5
Difference = 1	5	13	26
Difference = 0.5	13	44	97

Secondary

Subject reported assessments of nail health will be analyzed using descriptive statistics.

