12.2 Sample Size/Accrual Rate

With a total of 10 participants, 80 fingernails will be included in the treatment group, and 20 fingernails in the control group.

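### The unexplained 8:2 nail split gives about 51% power for a 0.5-point PRP-PPP difference at the plan's base case, and two separate before/after tests would often favour PRP when all nails change alike

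*Combined protocol and SAP*

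**What the plan says.** Section 6.1.2 randomises the ten fingernails of each participant to PRP or "platelet-poor plasma (placebo) treatment groups in a 8:2 ratio using a computer-generated randomization scheme". With ten participants, section 12.2 counts "80 fingernails will be included in the treatment group, and 20 fingernails in the control group".

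The only sample-size calculation is in section 12.1. It states that with "approximately 44 nails with PRP injection enrolled in the study, a score change of 0.5 from baseline" can be detected by a "paired two-sided t-test with 90% power at 0.05 significant level for PRP group". On the SD it says "The calculation assumed a standard deviation of 1 in scores", and it concedes that "there is not enough reference to assume an accurate standard deviation". A six-cell table of nail numbers follows. For a change of 0.5 it gives 13, 44 and 97 nails at SD 0.5, 1 and 1.5.

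The planned analysis in section 12.1 compares follow-up with baseline in the PRP nails and, separately, in the nails without PRP. It plans no test of PRP against PPP and does no sizing for the PPP nails. No section explains the 8:2 ratio. Section 3.2 only warns that the two control nails may give non-uniform results.

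**The concern.** The PPP nails are the study's only guard against change that affects all ten nails. Such change is plausible: sections 3.1 and 4.4 require participants to stop nail medication, moisturisers, oils and polish, and every nail fold is injected. Section 3.3 expects PPP not to promote growth, so the PPP nails are meant to show what happens without the active component.

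An 8:2 split gives the PRP side four times as many nails as its comparator. When each side is tested only against its own baseline, the larger set reaches significance more easily for the same true change. A result of PRP significant and PPP not significant would then look like a PRP effect when the real difference is in the number of nails. If a direct PRP-PPP contrast were added, 8:2 would also estimate it less precisely than the same 100 nails allow.

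**Working it through.** **Inputs from section 12.1:** two-sided alpha 0.05, change 0.5, SD 1 (range 0.5 to 1.5), 90% power, paired t-test. The SD is read as the SD of the change. The text says "With assumption of sd in range of 0.5 to 1, 13 to 97 nails would be needed", but the table puts 97 under SD 1.5, so 1.5 is taken as the upper end. **From sections 6.1.2 and 12.2:** 8 and 2 nails per participant, ten participants. **Assumed, because the documents do not give it:** within-person correlation of nail changes (ICC), shown from 0 to 0.7.

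**1. Reproducing the plan's figure.** Exact paired-t power uses the noncentral t with n−1 df and noncentrality 0.5·√n/SD. The smallest n with 90% power is 44 at SD 1. All six table cells reproduce (5, 13, 26; 13, 44, 97).

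**2. Power for a 0.5 change within one set, independent nails.**

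| Nails | SD 1 | SD 1.5 |
|---|---|---|
| 80 (PRP at 8:2) | 99.3% | 84% |
| 50 (either set at 5:5) | 93.4% | 64% |
| 20 (PPP at 8:2) | 56.5% | 29% |

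**3. Same true 0.5 change in both sets, so no PRP effect.** Chance that PRP is significant and PPP is not, SD 1, independent nails:
- 8:2: 0.993 × (1 − 0.565) = 0.43
- 5:5: 0.934 × (1 − 0.934) = 0.06

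Both sets come from the same ten people, so multiplying the two powers is exact only at ICC 0. Simulating the nail-level t-tests with correlated nails (SD 1) gives:

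| ICC | 8:2 | 5:5 |
|---|---|---|
| 0.3 | 37% | 7.5% |
| 0.5 | 33% | 6% |
| 0.7 | 30% | 5% |

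At 8:2 the reverse pattern (PPP only) is rare, at most 5% across the settings tried. At 5:5 the two patterns are equally likely.

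**4. Power for a PRP-PPP difference of 0.5, SD 1.**
Independent nails, 98 df:
- 8:2: SE = √(1/80 + 1/20) = 0.250, power 51%
- 5:5: SE = √(1/50 + 1/50) = 0.200, power 70%

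Within-participant contrast: SE = √[(1 − ICC)(1/a + 1/b)/10] for a PRP and b PPP nails, participant-level t on 9 df:

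| ICC | 8:2 SE, power | 5:5 SE, power |
|---|---|---|
| 0 | 0.250, 43% | 0.200, 60% |
| 0.3 | 0.209, 57% | 0.167, 76% |
| 0.5 | 0.177, 71% | 0.141, 88% |

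The SE ratio is √[(1/5 + 1/5)/(1/8 + 1/2)] = √(0.400/0.625) = 0.80 at any common ICC, provided the PRP effect is the same in everyone. If the effect varies between participants (assumed variance 0.1 to 0.25, residual variance 0.5), the contrast variance is proportional to that variance plus 0.5 × (1/a + 1/b):
- Effect variance 0.1: 0.4125 falls to 0.300, a 27% lower variance (SE 15% lower)
- Effect variance 0.25: 0.5625 falls to 0.450, a 20% lower variance (SE 11% lower)

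**5. Cost to the PRP-only mean.** With independent nails, see step 2. With correlated nails, the variance of a participant's PRP mean is [1 + (m − 1)·ICC]/m for m PRP nails:
- ICC 0.5: 0.5625 (m = 8) against 0.600 (m = 5); SE ratio √(0.600/0.5625) = 1.03
- ICC 0.3: 0.3875 against 0.440; SE ratio √(0.440/0.3875) = 1.07

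**The case against.** The best defence is that the extra PRP nails are a margin for an SD the plan admits it does not know. The primary endpoint (section 1.2.4) is defined on the PRP nails, only their change is powered, and at SD 1.5 the plan's own requirement is 97. Eighty already misses that and 50 misses it by more. This stands as a real cost of 5:5, although the plan does not offer it as the reason for 8:2.

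It is also fair that the root defect is the missing PRP-PPP comparison. A specified contrast would remove the misleading one-significant, one-not reading at any ratio. The size of that false pattern also depends on the unit of analysis: with participant means at ICC 0.5 it is 17% at 8:2 and 10% at 5:5. So the ratio change needs the contrast alongside it. The contrast alone, however, leaves the SE penalty of 8:2.

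A reader might infer four stronger things that the documents do not support:
- **That 20 control nails cannot show any difference.** With independent nails, 8:2 has about 98% power for a difference of 1.0 at SD 1, and for 0.5 at SD 0.5. Within-person pairing raises power if nail changes correlate.
- **That 5:5 is safe because 50 exceeds 44.** The 44 assumes independent nails. Fifty nails in ten people are worth 50/(1 + 4 × 0.3) = 23 independent nails at ICC 0.3 and 50/(1 + 4 × 0.5) = 17 at ICC 0.5. Eighty are worth only about 26 and 18.
- **That 5:5 equals recruiting 15.6 participants.** The figure 10 × 0.625/0.400 needs a constant PRP effect. With the varying effects in step 4 it is about 12.5 to 13.8.
- **That 8:2 weakens the committee's blinding.** An 80% chance of PRP applies equally to every nail and does not identify the two controls.

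**Conclusion.** The point holds as a worthwhile design improvement, not as a claim that the study cannot work. On the plan's base case, 8:2 gives the PRP side well over its stated requirement. It leaves the control side at 56% power for the same change and the PRP-PPP difference at about 51% for 0.5 points, with no stated reason. Combined with two separate before/after tests, this favours a spurious PRP-only finding about five or more times as often as 5:5 does, for nail-level tests at SD 1 with an ICC of 0 to 0.7.

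The conclusion rests on the 0.5 change and SD 1 of section 12.1 and on assumed correlations. Two limits apply. The PRP surplus does not exist at SD 1.5. And 5:5 is not sufficient for 90% power: with independent nails at SD 1, a 0.5 contrast would need 85 nails per group, or 53 control nails at 4:1.

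**What to change.** Allocate 5 PRP and 5 PPP nails per participant, for example by randomising one nail of each left/right pair of the same digit to each product. Amend sections 1, 1.1, 1.2.4, 3.1, 3.2, 6.1.2, 7.7, 7.11 and 12.2. In sections 12.1 and 12.4.1, make a within-participant PRP-PPP contrast the efficacy comparison and report the before/after changes descriptively. If 8:2 is kept, justify it against that contrast.

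State the downside in section 12.2. On the plan's independent-nail assumption, PRP-only power for a 0.5 change falls from 99% to 93% at SD 1 and from 84% to 64% at SD 1.5. The loss is small if nails within a person are correlated (SE up 7% at ICC 0.3, 3% at 0.5). Thirty fewer nails are exposed to PRP, which reduces the safety information.

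If enrolment has not begun, which the documents do not say, the cost is protocol wording and a new randomisation list. No participants or visits are added, and both products come from the same blood draw (section 7.6).

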6.1.3 Follow-up Phase

After visit 4 (week 12 - 14) is completed, the independent blinded endpoint committee will judge improvement of brittle nail syndrome based on high quality digital photography taken throughout the study.

7. Study Intervention

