3.1 Overall Design

This is a single center evaluation of 10 patients with signs and symptoms of brittle nails. Patients will be consented and 8/10 fingernails will be treated with PRP and 2/10 fingernails will be used as controls. Computer software will be used to randomly generate a randomization table for each participant. Randomization for each participant will be done on the same day of their first treatment, after all inclusion and exclusion criteria, including a negative histopathology report for onychomycosis are fulfilled. Blood will be drawn from a vein in the patient's arm into a 11 ml Eclipse PRP Tube. The blood is processed using a centrifuge machine from eclipse medical. After centrifugation, the platelet poor portion will be separated from the platelet-rich portion. The proximal nail folds are cleansed with alcohol. Using a 1ml syringe and 30g needle, 0.1-0.2 ml of platelet-rich plasma is injected into 8 proximal nail folds (treated nails), while 2 proximal nail folds (untreated nails) are injected with platelet-poor plasma. The study patients will be treated with PRP injections monthly for 3 months. Study patients may not have used any medications on the nails 3 months prior to the study or nail polish 1 month prior to the study. The patient must abstain from using any medication, moisturizers, oils, or nail polishes during the study period. The primary efficacy

endpoint will be the individual physician observed Physician Global Improvement Score (PGIA), which encompasses observed improvement of lamellar splitting, transverse splitting, ridges and longitudinal grooves, longitudinal splitting, and nail thickness of target nails. This is a PROBE design- Prospective Randomized Open Label Blinded Endpoint Design, i.e. Treatment is open label with respect to patient and investigators but is blinded to the endpoint committee. High quality images will be obtained utilizing a Canon camera and reviewed by an independent blinded endpoint committee (3 dermatologists with expertise in nails disease [name], [name], and [name] [name]) for PGIA (Physician Global Improvement Assessment. If necessary due to poor image quality (e.g. light source not properly deployed), exposure correction post-imaging may be applied to images that are deemed unsatisfactory. The present study Is not funded, Eclipse Medical provided the required PRP kits, including the sterile tubes.

PGA (Physician Global Assessment) Score:

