7.11 Measures to Minimize Bias: Randomization and Blinding

Computer software will be used to randomly generate a randomization table. 8/10 fingernails will be randomly allocated to treatment with PRP and the remaining 2 fingernails will receive injections with PPP. Randomization for each participant will be done on the same day of their first treatment, after all inclusion and exclusion criteria, including a negative histopathology report for onychomycosis are fulfilled. For the present study, treatment will be open label with respect to patient and investigators but is blinded to the endpoint committee. High quality images will be obtained utilizing a Canon camera and reviewed by an independent blinded endpoint committee (3 dermatologists with expertise in nails disease [name], [name], and [name] [name]) for PGIA (Physician Global Improvement Assessment.

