9.2.1.1 Assessment

9.2.1.2 Method of Assessment

9.2.1.3 Timing of Assessment

10. Measurement of Effect

PGA (Physician Global Assessment) Score:

The Principal Investigator will utilize the Physician Global Assessment (PGA) score for screening purposes during the screening/baseline visit to determine eligibility. The PGA will be comprised of five components: lamellar splitting, transverse splitting, ridging and longitudinal groove, longitudinal splitting, and nail thickness. Lamellar splitting, which represents onychoschizia, is defined as distal furrows or splits encompassing the distal nail plate involving the complete free edge of the nail plate. The second component, transverse splitting, is described as horizontal splitting from the free edge of the nail plate- with at least 2 or 3 horizontal splits of the distal nail plate. The third component, ridging and longitudinal grooves, is defined by at least 50% of the nail plate showing deep ridges and corresponding grooves. The fourth component, longitudinal splitting, which represents onychorrhexis, is defined as at least one deep longitudinal split of the entire nail plate. The fifth component, nail thickness, is defined by a clearly visible change in nail thickness. The presence of each of these components during the screening/baseline visit will represent 1 point on a scale. The inclusion criterion requires patients to have a score of at least 2 out of a maximum of 5 points. An independent blinded endpoint committee will assess change from baseline based on the PGA.

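### Committee blinding covers treatment only and visit order is not masked, so a tendency to rate later photographs better would pass uncancelled into the within-arm primary tests

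*Combined protocol and SAP*

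**What the plan says.** **Blinding.** Section 7.11 states that "treatment will be open label with respect to patient and investigators but is blinded to the endpoint committee". The Study Design entry in the Protocol Summary and sections 3.1 and 3.2 say the same. All four concern treatment. None mentions visit, date or image order.

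**The readers' task.** Under section 6.1.3 the committee, after Visit 4, "will judge improvement of brittle nail syndrome based on high quality digital photography taken throughout the study". Section 3.1 describes the PGIA as a score "which encompasses observed improvement of lamellar splitting, transverse splitting, ridges and longitudinal grooves, longitudinal splitting, and nail thickness of target nails". Section 10 words the task differently: "An independent blinded endpoint committee will assess change from baseline based on the PGA". Section 10.1 also names change in PGA, whereas section 1.2.4 names change in PGIA.

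**Image handling.** Section 3.1 provides that, where image quality is poor, "exposure correction post-imaging may be applied to images that are deemed unsatisfactory". It does not say who does this, by what rule, or whether both images of a pair are treated alike.

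**Primary comparison.** Section 12.1 gives the PGIA, "which will be compared between follow-up point (week 12 - 14) and baseline point for nails with PRP injection", and then a second comparison of follow-up with the "baseline point for nails without PRP injection". Sections 12.4.1 and 12.4.2 only refer back to 12.1. No PRP-versus-PPP test is specified.

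**The concern.** Blinding readers to arm protects a comparison between arms. If readers expect nails to look better at the end of a treatment study, both arms gain the same shift, and it drops out of a PRP-minus-PPP difference. The specified tests take no such difference. Each compares late with early images within one arm, so the whole shift enters the estimate.

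The task makes this a practical risk. Rating improvement needs a known starting point, unless each image is scored separately and the scores are subtracted, and no such procedure is described.

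Two things are at stake. The PRP test could be significant with no true change. And because the arms have 80 and 20 nails, the same shift would reach significance far more often for PRP than for PPP, which could be misread as a PRP-specific effect.

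**Working it through.** **Inputs.** From section 12.1: paired two-sided t-test, alpha 0.05, 90% power, change 0.5, SD 1, with 0.5 and 1.5 also tabulated. From section 12.2: 80 PRP and 20 PPP nails from 10 participants. Assumed, because the documents give no value: the rating shift b and the within-patient correlation (ICC).

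**Formula.** Rejection probability = P(|T| > t(0.975, n−1)), where T is noncentral t with n−1 degrees of freedom and noncentrality (mean change)·√n / SD. SD is taken as the SD of the paired change.

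**The plan's own figure.** For change 0.5 and SD 1, n = 44 gives noncentrality 0.5·√44 = 3.317 and power 0.9000. The stated 44 is reproduced, as are all six table cells (5, 13, 26; 13, 44, 97).

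**False-positive rate with a shift.** True change 0, SD 1, independent nails, mean rated change b:

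| b | b·√80 | PRP test rejects | b·√20 | PPP test rejects |
|---|---|---|---|---|
| 0 | 0 | 5.0% | 0 | 5.0% |
| 0.1 | 0.894 | 14.3% | 0.447 | 7.1% |
| 0.2 | 1.789 | 42.4% | 0.894 | 13.6% |
| 0.3 | 2.683 | 75.5% | 1.342 | 24.7% |

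**Other SDs in the plan's table**, PRP test at b = 0.2:
- SD 0.5: noncentrality 1.789/0.5 = 3.578, rejects in 94.2%.
- SD 1.5: noncentrality 1.789/1.5 = 1.193, rejects in 21.8%.

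**PRP significant and PPP not**, if the two tests are independent (SD 1): 0.143 × 0.929 = 13%; 0.424 × 0.864 = 37%; 0.755 × 0.753 = 57%.

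**Correlated nails.** Simulation of 20,000 trials, 10 patients with 8 PRP nails each, total SD 1, no true effect, nail-level test:
- ICC 0.3: rejects in 27% with b = 0 and 48% with b = 0.2.
- ICC 0.5: rejects in 36% with b = 0 and 52% with b = 0.2.

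Hand check for ICC 0.3: the design effect is 1 + 7 × 0.3 = 3.1, with square root 1.761. The effective critical value is 1.990/1.761 = 1.130, so with b = 0 the two-sided normal tail is about 26%. With b = 0.2 the mean moves to 1.789/1.761 = 1.016, and the rejection probability is about 47%. Both agree with the simulation.

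**Between-arm contrast.** In the same simulation, a within-patient PRP-minus-PPP t-test on 10 patients rejects in 4.8% to 5.2% for b of 0, 0.2 and 0.5 and ICC of 0, 0.3 and 0.5. A shift common to both arms cancels.

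**The case against.** **The documents do not say that readers know the visit order.** This is correct. A reader of the plan might infer that the committee is told which image is baseline, but no sentence says so. Section 10's wording and section 12.1's paired test can be read as separate scoring at each time point followed by subtraction. Sections 6.1.3 and 3.1, which speak of judging or observing improvement, point the other way. What stands is that masking of order is nowhere stated and the described task implies that order is recognisable. Even separate scoring would not help unless visit is hidden.

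**Exposure correction.** It is tempting to infer that open-label staff adjust images, and do so differently by visit. The text names nobody and limits correction to poor image quality. The supportable point is only that no rule or masking is given.

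**The size.** One might read 5% rising to 42% as the trial's expected error. It is not an estimate: the shift is assumed, the result depends heavily on SD, and the 5% starting point needs independent nails. With ICC 0.3, a 0.2 shift adds about 21 percentage points (27% to 48%), not 37.

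**The root cause is the missing between-arm test.** Largely true. Masking order leaves natural course, or the effect of abstaining from polish, moisturizers and oils (section 4.4), inside a before-after test. That makes masking insufficient, but not unnecessary: it is the only protection against this bias while the within-arm tests remain primary.

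**Conclusion.** The point holds as a weakness in how the primary score is obtained. Committee blinding is defined for treatment alone, visit order is unmasked in the text, and the primary tests are of a kind that arm blinding does not protect. A shift of 0.2 points, less than half the 0.5-point change the plan is powered for, would make the PRP test significant in 42% of trials with no true effect, under the plan's SD of 1 and independent nails. Over the plan's tabulated SDs of 0.5 to 1.5 that figure runs from 94% to 22%. These are sensitivity figures; whether any shift would occur, and how large, cannot be learned from the documents. Masking takes this source of bias away, but the nail-level test would still exceed 5% if nails within a patient are correlated. The change should be made before images are read.

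**What to change.** **Sections 6.1.3 and 7.11.** Code the Visit 1 (pre-injection) and Visit 4 images, remove dates, and show them in random order to the three existing readers, without visit or arm. Then use one of two procedures:
- each image is scored separately and the analyst computes the change; or
- if the PGIA stays a comparative rating, readers rate the masked pair (which image is better, and by how much) and the analyst assigns direction afterwards.

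**Sections 1.2.4, 10, 10.1 and 12.1.** State which score is primary, PGIA or change in PGA. Choosing per-image PGA scoring is an endpoint decision and should be recorded as one.

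**Section 3.1.** Apply any exposure correction by a fixed rule to both images of a pair, say who does it, and keep the originals.

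**Cost.** No extra visits, participants or readers; the images are already scheduled. Someone must prepare the coded files. Separate scoring doubles the ratings, from 100 nails × 3 readers = 300 to 600. The PGA thickness item, which is itself worded as a change, would need wording that can be scored from one image. The masked-pair option keeps one rating per nail.

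**Limit.** Masking does not remove other changes common to both arms. Only a within-patient PRP-versus-PPP contrast does that, and it should be considered alongside.
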